| 
Number of Subjects (planned):
 | 
Approximately 32 subjects in each of the SAD and MAD portions will be enrolled in the study, with 8 subjects per cohort, randomized at a 3:1 ratio (6 active and 2 placebo), for a total of 64 subjects in the study. The exact number of subjects enrolled is dependent on whether any dose levels are to be expanded due to the occurrence of dose-limiting toxicities (DLTs).
 |

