4.3 Dose Escalation

The single dose escalation scheme will test fill doses of 6.25 mg to 50 mg over 4 dose levels, and the multiple dose escalation scheme will test fill doses of 6.25 mg to 50 mg given thrice weekly (tiw) for 4 weeks ([Table 1](#)). As described in Section 2.2.1, the dose delivered to subjects via the eFlow device is < 80% of the fill dose, hence the delivered doses that correspond to the dose escalation schemes are shown in [Table 1](#).

Table 1: Dose Escalation

| Dose Cohort | Fill Dose (mg) | Estimated Exposure Dose < 80% of Fill Dose (mg) |
|-----------------------------------------------------------------|----------------|----------------------------------------------------|
| Single Dose Cohorts | | |
| 1 | 6.25 | 5 |
| 2 | 12.5 | 10 |
| 3 | 25 | 20 |
| 4 | 50 | 40 |
| Multiple Dose Cohorts (administered tiw for 4 Weeks) | | |
| 5 | 6.25 | 5 |
| 6 | 12.5 | 10 |
| 7 | 25 | 20 |
| 8 | 50 | 40 |

tiw = thrice weekly (three times per week)

Dose escalation will initially proceed in single subject cohorts from fill dose level 1 (6.25 mg) to fill dose level 4 (50 mg).

Initiation of MAD Cohort 5 will be based on the safety profile of SAD Cohort 2. Initiation of Cohort 6 will be based on the safety profiles of Cohorts 3 and 5. Similarly, initiation of Cohort 7 will be based on the safety profiles of Cohorts 4 and 6, and finally, the initiation of Cohort 8 will be based on the safety profile of Cohort 7. The first dose between subjects in each cohort must be separated by a minimum of 4 hours.

For the single dose cohorts 1 to 4, dose escalation to the next cohort may occur upon recommendation of the DSMC after the subjects have been observed for at least 7 days and no DLTs have occurred or, if a DLT has occurred, per the dose escalation rules in Section 4.5. For the multiple dose cohorts 5 to 8, dose escalation to the next cohort may occur upon recommendation of the DSMC after the subjects have been observed for at least 7 days after the last dose (End of Treatment Visit). If a DLT occurs in any cohort, the AEs and DLTs will be reviewed by the Investigator and the DSMC before dosing can continue in that cohort. In addition, if ≥ 2 subjects experience a decrease in absolute FEV₁ of $\geq 15\%$ from baseline in any cohort, the data will be reviewed by the DSMC before dose escalation can continue.

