13.2 Determination of Sample Size

This is a Phase 1 safety study designed to evaluate the safety, tolerability and PK of QR-010. The sample size is not based on power calculations. It is chosen based on clinical experience and considered to be adequate to fulfill the objectives of the study.

Approximately 64 subjects will be enrolled in the study, with 8 subjects per cohort (6 QR-010 and 2 placebo), 32 each in the SAD and MAD portions of the study. The exact number of subjects enrolled is dependent on whether any dose level are to be expanded due to the occurrence of DLTs.

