## 2.4. Randomization Methodology

Within each dosing cohort, subjects will be randomized 3:1, QR-010 to placebo.

The randomization is performed using a centralized interactive web response system (IWRS).

Study drug will be administered in a double-blind fashion. Study drug and placebo are both clear, colorless, and odorless aqueous solutions. Subjects, Investigators and study site staff will be blinded to treatment assignment. However, due to the requirement for study pharmacist(s) to prepare the various study drug dilutions depending on the dosing cohort to which a given study subject is assigned, the study pharmacist(s) will be unblinded to treatment assignment.

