##### **4.8.1.1. ppFEV1 (%)**

The ppFEV1 value, absolute change from baseline and % change from baseline (relative change) will be presented descriptively over time (considering all time points from the visit windows for this parameter), per treatment group.

Graphical representation may be provided (mean change+ 95% CI overtime). Particularly a zoom on the data for the first 24 hours following first dose will be given).

[figure not shown]
In order to assess differences versus placebo a mixed model with repeated time measures on the change from baseline ppFEV1 as outcome variable and including treatment, baseline ppFEV1 value, time and interaction between time and treatment as covariates. By default, an unstructured covariance matrix will be used, unless convergence issue, in which case other covariance matrix will be explored. Adjusted means and corresponding confidence interval will be presented.

For Day 1, several spirometry assessments (pre and post dose) are planned. Subjects usually suffer from fatigue due to the multiple assessments, resulting in low post-dose values of FEV1. Additionally, inhalation of the IMP may transiently impact the spirometry results. Thus the following time points will be included in the repeated measures analysis: Baseline, Day 2, Day 4 and Day 8, using the time windows.

Analyses to explore the dose response using the MCPMod methodology will be followed. A set of dose-response models will be tested including change from baseline ppFEV1 at Day 4 as dependent variable, the treatment as factor (0, 6.25, 12.5, 25, 50 mg) and ppFEV1 value at baseline (see Table 25 and Figure 2). The presence of a dose-response signal will be demonstrated if at least one of the candidate models is significant, adjusting for the different models (overall alpha=5% two-sided). Due to the small sample size, overall alpha for this exploratory dose-response analysis may be adapted. If a model is selected, an estimate of the minimum effective dose will be performed. Thresholds of 3%, 5% and 7% will be tested as sizes of interest of treatment effect (differences versus placebo).

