#### Cystic Fibrosis Questionnaire- Revised Respiratory Symptoms Score (CFQ-R RSS)

The CFQ-R RSS is calculated based on mean score of Questions 40 to 46 excluding question 43 as below if  $\leq 3$  item scores are missing:

Assuming a coding of 1 to 4 with categories such as

1=A great deal / Always

2=Somewhat / Often

3=A little / Sometimes

4=Not at all / Never,

$$\text{CFQ-R RSS} = \text{mean} [(\text{resp40}, \text{resp41}, \text{resp42}, \text{resp44}, \text{resp45}, \text{resp46})-1]/3*100;$$

The score will be missing if more than three of the six scores are missing.

Descriptive summary overtime will be provided for the values and change from baseline at each time point following the time windows, by treatment group.

A mixed model analysis with repeated time measures on the change from baseline of CFQ-R RSS as outcome variable, including treatment, baseline CFQ-R RSS value, time and interaction between time and treatment as covariates will be performed. By default, an unstructured covariance matrix will be used, unless convergence issue occurs, in which case other covariance matrix will be explored. Adjusted means and corresponding confidence interval will be presented. The following time points will be included in the repeated measures analysis: Baseline, Day 15, Day 33 and Day 54. Differences versus placebo will be estimated at Day 33 and Day 54.

A dose-response analysis using MCPMOD methodology will be performed with change from baseline of CFQ-R RSS at Day 33 as dependent variable, the treatment (0, 6.25, 12.5, 25, 50 mg) and CFQ-R RSS at baseline as factors. Thresholds of +4, +5, +8 and +10 will be tested as sizes of interest of treatment effect.

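### Placebo is pooled over four sequential, dose-ordered cohorts with no cohort term, so the exploratory efficacy models as specified do not separate dose from between-cohort drift

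*Protocol*

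**What the plan says.** **Randomisation.** SAP 2.4 states: "Within each dosing cohort, subjects will be randomized 3:1, QR-010 to placebo". Protocol 13.3.1 agrees, and Protocol 1.0 plans enrolment "with 8 subjects per cohort, randomized at a 3:1 ratio (6 active and 2 placebo"; Protocol 13.2 gives the same split.

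**Order.** Protocol 4.3 says that "dose escalation to the next cohort may occur upon recommendation of the DSMC after the subjects have been observed for at least 7 days"; for MAD the 7 days run from the last dose. Cohort 6 needs Cohorts 3 and 5, Cohort 7 needs Cohorts 4 and 6, and Cohort 8 needs Cohort 7. Within each part, dose rank is therefore calendar rank.

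**Analysis.** SAP Tables 3 and 4 show one placebo column per part. The SAD ppFEV1 mixed model (SAP 4.8.1.1) contains treatment, baseline, "time and interaction between time and treatment as covariates". The MAD models for ppFEV1, glucose, CFQ-R RSS and weight (SAP 4.8.2) have the same structure. MCPMod has a single zero-dose level; for CFQ-R RSS it uses "the treatment (0, 6.25, 12.5, 25, 50 mg) and CFQ-R RSS at baseline as factors". The only further covariates are baseline *Pseudomonas* and CF-related diabetes, each in a sensitivity analysis. No cohort, period or calendar term appears, and the post hoc plan adds none. The SAP does not itself call placebo pooled. That follows from the single column and the single zero-dose level.

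**The concern.** Randomisation protects the comparison of 6 active with 2 placebo subjects inside a cohort. The planned contrast for each dose uses 8 placebo subjects, 6 of them enrolled in other cohorts at other times. If mean change from baseline shifts between cohorts (season, sites, case mix), the shift enters the dose contrast. Because dose follows calendar order, a steady upward shift makes the lowest dose look worse and the highest look better. That is the monotone shape the candidate models in SAP Table 25 look for. A downward shift would hide a real effect.

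The protocol contains routes for such a shift. The study period is 24 months. A subject may choose SAD or MAD when both are open (13.3.1), and SAD completers may enter MAD after 90 days (5.5.1). What is at stake is the exploratory dose-response signal and the minimum effective dose estimate built on it in SAP 4.8.1.1; Protocol 4.1.3 says the observed changes may inform later studies. No planned output shows placebo by cohort, so a reader could not check.

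**Working it through.** **Inputs from the documents.** 6 active and 2 placebo per cohort, four cohorts per part (Protocol 1.0, 13.2); the model terms above; ppFEV1 thresholds of 3, 5 and 7 (SAP 4.8.1.1).

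**Assumptions.** No true drug effect; normal errors; a linear drift in change from baseline totalling D from first to last cohort, with D = 3 to 5 ppFEV1 points; SD 6 to 8; no expanded cohorts or replacements; baseline covariate left out of the simulations. The documents give neither D nor SD.

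**1. The plan's own figure.** 8 × (6 + 2) = 64, 4 × 8 = 32 per part, and 6:2 = 3:1. All reproduce. There is no power figure to reproduce: "The sample size is not based on power calculations" (Protocol 13.2).

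**2. Concurrent share.** Placebo per part is 4 × 2 = 8. For any dose 2/8 = 25% are concurrent and 75% are not.

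**3. Bias per dose.** Centred cohort effects are −D/2, −D/6, +D/6 and +D/2. Pooled placebo has 2 subjects from each cohort, so its mean effect is 0 and each dose keeps its full cohort effect as bias. At D = 5 this is −2.5, −0.83, +0.83 and +2.5 points for 6.25, 12.5, 25 and 50 mg. With a fixed cohort term it is 0.

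**4. Linear dose trend, nominal 5% two-sided (40,000 simulated trials per setting).**

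| D | SD | Rejects, pooled placebo | Rejects, cohort in model |
|---|---|---|---|
| 3 | 8 | 8% | 5% |
| 3 | 6 | 10% | 5% |
| 5 | 8 | 13% | 5% |
| 5 | 6 | 20% | 5% |

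Hand check for the last row. The sum of squares of dose is 6 × 3320.31 − 32 × 17.578² ≈ 10,034, so the slope SE is 1/√10,034 = 0.00998 per unit SD. The drift adds 6 × 23.96 × D / 10,034 = 0.0143 × D per mg to the slope. With D = 5 and SD = 6 the shift is 0.0716 / (6 × 0.00998) ≈ 1.2 standard errors. A normal approximation then gives about 22%, consistent with the simulated 20%, in which the drift also inflates the residual variance.

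**5. MCPMod with the five Table 25 shapes, nominal 2.5% one-sided (50,000 trials per setting).** For a drift of 0, 0.1, 0.25 and 0.5 SD per cohort step, the false-signal rate is 2.5%, 6%, 15–16% and 49–50%. D is three steps, so D = 3 with SD 8 is 0.125 SD per step and D = 5 with SD 6 is 0.28 SD per step. The settings in step 4 thus lie roughly between the second and third values. The log-linear offset is not given; 0.5 and 1.0 gave nearly the same results.

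**6. Cost of blocking on cohort.**
- One dose against placebo: √(1/6 + 1/8) = 0.540 SD pooled; √(1/6 + 1/2) = 0.816 SD within cohort; ratio 1.51.
- Linear slope: the within-cohort sum of squares is 1.5 × 3320.31 = 4,980, so the SE is 0.01417 against 0.00998; ratio 1.42.
- 95% half-width for one dose: 1.108 × SD pooled (27 df) and 1.685 × SD blocked (24 df). For SD 6 to 8 that is 6.6 to 8.9 points against 10.1 to 13.5.

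**7. Time between cohorts.** On the scheduled MAD calendar, Day 1 to the Day 33 visit is 768 hours, or 32 days. Three gaps give at least 96 days from Cohort 5 to Cohort 8.

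**The case against.** - **The analyses are exploratory.** The protocol says the study is not powered for efficacy (2.2, 4.1.3) and treats any inference as hypothesis generation (13.4). The SAP applies no multiplicity adjustment (4.2.6). This stands and limits the weight of the point. It does not remove it, since SAP 4.8.1.1 still sets a rule for calling a dose-response signal and then estimates a minimum effective dose.
- **Drift is limited by design.** The outcome is within-subject change over 8 days (SAD) or 54 days (MAD), adjusted for baseline, so cohort differences in starting level are largely absorbed. Day −1 FEV1 must be within 10% of screening (5.3), infection or a pulmonary therapy change in the prior 30 days excludes (5.4), background therapy is held constant (6.3.1, 8.10), exacerbations needing antibiotics lead to withdrawal (5.5.1), and all sites are expected to enrol all cohorts (13.3.1). This stands in part: it makes large drift less likely but does not exclude drift in change itself. A false monotone trend also needs roughly monotone drift, and seasonal drift need not be monotone.
- **The size is assumed.** True. The rates in the working are conditional illustrations, not estimates for this trial.
- **Pooling buys precision.** With 2 placebo subjects per cohort, a cohort-adjusted comparison is weak. This stands and is the reason to keep pooled placebo as the main analysis.

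**Conclusion.** The point holds for the placebo-controlled exploratory efficacy analyses in SAP 4.8. As written, they do not separate dose from between-cohort drift in change from baseline. Under the assumed drift of 3 to 5 points and SD of 6 to 8, the false-positive rate of a 5% linear trend test is about 8% to 20%, and the bias at the lowest and highest dose is up to 2.5 points in opposite directions, against thresholds of 3, 5 and 7. With no drift, the pooled analysis is valid and more precise.

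A reader might infer three stronger things that the documents do not support:

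- *That dose and drift cannot be told apart in this trial.* Every cohort has its own placebo subjects, so a cohort term is estimable. The gap is in the specified analysis, not the design.
- *That the within-cohort structure is never used.* The DSMC reviews unblinded safety data cohort by cohort (Protocol 12.1, SAP 2.5.2).
- *That escalation or the MTD is compromised.* The DLT rule counts events in subjects receiving QR-010 (Protocol 4.5, SAP 2.3) and makes no placebo comparison.

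**What to change.** Keep the pooled-placebo analysis as the main one and add the following to SAP 4.8:

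1. **A cohort-blocked sensitivity analysis** of the dose comparisons and MCPMod at the key visits for ppFEV1, and in MAD also CFQ-R RSS, weight and glucose. A per-visit ANCOVA with baseline, treatment and cohort as a fixed factor is enough; cohort-by-time in the mixed model is the alternative. A cohort main effect alone in the mixed model is not enough. In a two-visit check with D = 5 and drift at the second visit only, it left a bias of ±1.25 of the original ±2.5 there. Cohort-by-time is demanding in MAD: ten post-baseline visits with an unstructured covariance already need 10 × 11 / 2 = 55 covariance parameters from about 32 subjects. The per-visit ANCOVA is therefore the more practical choice.
2. **A table of placebo change from baseline by cohort**, for each part.
3. **Reporting:** cohort-adjusted estimates with confidence intervals beside the pooled ones, and a statement that the pooled result assumes no between-cohort drift.

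Do not use a rule that calls a signal supported when the adjusted estimate has the same sign. The two slopes share data (correlation about 0.7). At D = 5, such a rule passed 92.5% (SD 6) and 95.3% (SD 8) of false pooled signals.

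The cost is SAP text, one repeat run and one table. Intervals are wider in the sensitivity run only: SE about 1.5 times larger for one dose against placebo and about 1.4 times for the linear slope. Data collection, dosing and escalation rules do not change.

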Appendix 1: Schedule of Assessments83
Appendix 2: Schedule of Laboratory Tests91
Appendix 3: Adult CFQ-R (English).....99

LIST OF ABBREVIATIONS AND DEFINITIONS OF TERMS

| Abbreviation or Term | Definition/Explanation |
|-----------------------------|--------------------------------------------------------------------------------------------------------------------------------------------------------------------------------------------------------------|
| ADL | Activities of Daily Living |
| AE | Adverse Event |
| ALT (SGPT) | Alanine aminotransferase (Serum Glutamic Pyruvic Transaminase) |
| ANOVA | Analysis of Variance |
| AON | Antisense Oligonucleotide |
| AST (SGOT) | Aspartate aminotransferase (Serum Glutamic Oxaloacetic Transaminase) |
| ATP | Adenosine triphosphate |
| ATS | American Thoracic Society |
| AUC | Area Under the Curve |
| AUC _{0-∞} | Area under the curve from time zero to infinity |
| AUC _{0-t} | Area under the curve from time zero to the final time point |
| bpm | Beats per minute; Breaths per minute |
| bps | Base pairs |
| BUN | Blood Urea Nitrogen |
| C | Celsius |
| CBC | Complete Blood Count |
| CF | Cystic Fibrosis |
| CFR | Code of Federal Regulations |
| CFQ-R | Cystic Fibrosis Questionnaire-Revised |
| CFQ-R RSS | Cystic Fibrosis Questionnaire-Revised Respiratory Symptoms Score |
| CFTR | Cystic Fibrosis Transmembrane Conductance Regulator |
| CH50 | Total Complement |
| CL | Serum Clearance |
| Clinically significant | An abnormal finding/laboratory value that indicates a new disease process, an exacerbation or worsening of an existing condition, or requires further action(s) to be taken (eg, initiation of new therapy). |
| C _{max} | Maximum Concentration |
| C _{min} | Minimum Concentration |
| CRF, eCRF | Case Report Form, Electronic Case Report Form |
| CRO | Contract Research Organization |
| CRP | C-reactive protein |
| CSR | Clinical Study Report |

| Abbreviation or Term | Definition/Explanation |
|-----------------------------|---------------------------------------------------------------|
| CTCAE | Common Terminology Criteria for Adverse Events |
| CXR | Chest Xray |
| DAT | Direct Antiglobulin Test |
| dL | Deciliter |
| DLT | Dose-Limiting Toxicity |
| DP | Drug Product |
| DS | Drug Substance |
| DSMC | Data Safety Monitoring Committee |
| EC, IEC | Ethics Committee, Independent Ethics Committee |
| ECG | Electrocardiogram |
| EMA | European Medicines Agency |
| ENaC | Epithelial Sodium Channel |
| ERS | European Respiratory Society |
| ESR | Erythrocyte Sedimentation Rate |
| ET | Early Termination |
| EU | European Union |
| F | Fahrenheit |
| FDA | Food and Drug Administration |
| FEF ₂₅₋₇₅ | Forced Expiratory Flow between 25 and 75% of the FVC |
| FEV ₁ | Forced Expiratory Volume in 1 second |
| FVC | Forced Vital Capacity |
| g | Gram |
| GCP | Good Clinical Practice |
| Hct | Hematocrit |
| HED | Human Equivalent Dose |
| Hgb | Hemoglobin |
| HHS | Health and Human Services |
| HIPAA | Health Information Portability and Accountability Act of 1996 |
| HR | Heart Rate |
| ICH | International Conference on Harmonisation |
| INR | International Normalized Ratio |
| IRB | Institutional Review Board |

| Abbreviation or Term | Definition/Explanation |
|-----------------------------|--------------------------------------------------------------------------|
| IUD | Intrauterine Device |
| IUS | Intrauterine hormone-releasing system |
| IV | Intravenous |
| IWRS | Interactive web response system |
| kg | Kilogram |
| L | Liter |
| LABA | Long-acting β -agonist |
| LDH | Lactic Dehydrogenase |
| LLQ | Lower Limit of Quantitation |
| MAD | Multiple Ascending Dose |
| MDD | Maximum Deliverable Dose |
| mRNA | Messenger Ribonucleic Acid |
| μ g | Microgram |
| mg | Milligram |
| mL | Milliliter |
| mmHg | Millimeters of Mercury |
| MRSD | Maximum Recommended Starting Dose |
| MTD | Maximum Tolerated Dose |
| NCI CTCAE | National Cancer Institute-Common Terminology Criteria for Adverse Events |
| N | Normal |
| ng | Nanogram |
| NOAEL | No Adverse Effect Level |
| NPD | Nasal Potential Difference |
| OTC | Over the Counter |
| PCL | Periciliary Layer |
| PD | Pharmacodynamics |
| PDD | Pulmonary Deposited Dose |
| PE | Physical examination |
| pH | Hydrogen ion concentration |
| PK | Pharmacokinetics |
| POC | Proof of Concept |
| Post | After |

| Abbreviation or Term | Definition/Explanation |
|-----------------------------|-----------------------------------------------|
| Pre | Before |
| PS | Phosphorothioate |
| PT | Prothrombin Time, Preferred Term |
| PTT | Partial Thromboplastin Time |
| QTc | QT Interval-Corrected |
| RBC | Red Blood Cell |
| RNA | Ribonucleic Acid |
| SABA | Short-acting β -agonist |
| SAD | Single Ascending Dose |
| SAP | Statistical Analysis Plan |
| SAE | Serious Adverse Event |
| SD | Standard Deviation |
| SGOT (AST) | Serum Glutamic Oxaloacetic Transaminase |
| SGPT (ALT) | Serum Glutamic Pyruvic Transaminase |
| SOC | System Organ Class |
| SOP | Standard Operating Procedure |
| SUSAR | Suspected Unexpected Serious Adverse Reaction |
| $t_{1/2}$ | Terminal elimination phase half-life |
| TEAE | Treatment-Emergent Adverse Event |
| tiw | Thrice Weekly (three times per week) |
| TK | Toxicokinetic |
| TLF | Tables, Listings and Figures |
| t_{max} | Time to maximum concentration |
| ULN | Upper Limit of Normal |
| US | United States |
| WBC | White Blood Cell |
| WT | Wild Type |

2.0 INTRODUCTION

ProQR Therapeutics (ProQR, the Sponsor) is developing an antisense oligonucleotide (AON) product, QR-010, for the chronic treatment of patients with cystic fibrosis (CF) that is associated with either a compound hetero- or homozygous genotype for the absence of phenylalanine at position 508 ($\Delta F508/p.Phe508del$) on cystic fibrosis transmembrane conductance regulator (CFTR)-encoded ribonucleic acid (RNA). QR-010 is a single-stranded RNA oligonucleotide that is complementary to the $\Delta F508$ region on the RNA transcription product of the CFTR gene. Translation of the repaired CFTR encoded RNA should result in [REDACTED] normal CFTR protein. The intended route of clinical administration is oral inhalation (inhalation) of nebulized QR-010 solution.

Cystic Fibrosis Associated with $\Delta F508$ CFTR Genotype

[figure not shown]
Cystic fibrosis is an autosomal recessive disorder that is caused by a mutation in a gene that encodes CFTR, a membrane protein with pleiotropic functions. CFTR regulates the surface liquid layer and is found in the epithelial cells of the respiratory, gastrointestinal, and biliary systems; male reproductive tract; and exocrine sweat glands. This protein consists of 1480 amino acids that are divided into five domains, two of which cross the membrane to form a bidirectional, trans-membrane chloride channel (Riordan *et al.*, 1989). Although CFTR functions primarily as a chloride channel, it has many other regulatory roles that affect the CF phenotype. These include inhibition of sodium transport through the epithelial sodium channel (ENaC), regulation of the outwardly rectifying chloride channel, regulation of adenosine triphosphate (ATP) channels, regulation of intracellular vesicle transport, acidification of intracellular organelles, and inhibition of endogenous calcium-activated chloride channels. The CFTR protein is also involved in bicarbonate–chloride exchange. A deficiency in bicarbonate secretion leads to poor solubility and aggregation of luminal mucins. Lack of CFTR function results in the multi-organ system clinical syndromes described in patients with CF (Collawn *et al.*, 2012; Mehta, 2005; O’Sullivan & Freedman, 2009; Quinton, 1999; Reisin *et al.*, 1994; Vankeerberghen *et al.*, 2002).

The CFTR gene is encoded on chromosome 7 (Chr 7 117,120,017 through to 117,308,715). The transcription product of the CFTR gene (189 kb) is a messenger RNA (mRNA) (6.1 kb) that is translated into the CFTR protein. A patient with a CF phenotype has a CFTR gene mutation on both alleles and may be homozygous for a single mutation or compound heterozygous with a different mutation on each allele. There are nearly 2000 CFTR gene variants. However, only 159 variants have an allele frequency $\geq 0.01\%$ and 127 of those 159 variants meet both the clinical (pilocarpine iontophoresis sweat chloride test) and functional (affects RNA quality/quantity or CFTR protein) criteria to cause CF. Together, these 159 variants account for 96.4% of identified cystic fibrosis alleles. The $\Delta F508$ mutation is the most common allelic mutation and accounts for about 66-70% of identified mutated alleles in northern European and North American populations. According to the Cystic Fibrosis Foundation National Patient Registry Annual Data Report (2012), a total of 23,053 CF patients (86.7% of the CF population in the US) in the US

had one or two copies of the $\Delta F508$ mutation (O'Sullivan & Freedman, 2009; Sosnayet *et al.*, 2013).

The various CFTR mutations are often classified into 5 specific functional classes, as shown in Figure 1. The $\Delta F508$ mutation (hetero- or homozygous) is a Class II CFTR functional mutation that is characterized by defective CFTR processing; the gene is transcribed but the translated protein product is not trafficked through the endoplasmic reticulum and is degraded before reaching the cell surface. The $\Delta F508$ mutation results in a CFTR protein that is mis-folded, which results in ubiquitination and degradation. As a result, little, if any, CFTR reaches the plasma membrane. QR-010 has the potential to treat all CF patients with the $\Delta F508$ mutation on at least one allele (O'Sullivan & Freedman, 2009; Pasyk & Foskett, 1995; Zamecnik *et al.*, 2004).

Figure 1: Classes of CFTR Mutations

Classes of CFTR mutations. Categories of CFTR mutations with mutations resulting in no synthesis (Class I), defective processing (Class II), defective regulation (Class III), defective or deficient conduction (Class IV), and reduced amount of functional CFTR protein (Class V).

Source: Gelfond & Borowitz, 2013

The most common cause of death in patients with CF is respiratory failure due to progressive loss of lung function and/or pulmonary disease (Davies *et al.*, 2007). There are several hypotheses regarding the mechanism by which the $\Delta F508$ mutation leads to the multi-organ system CF phenotype and progressive loss of function, however the causal relationship between CFTR dysfunction and the CF phenotype is well established (Sosnay, 2013). In the simplest pathophysiological scenario, functional CFTR is either absent or substantially reduced at the apical membrane; the absence of functional CFTR at the apical membrane of ciliated airway epithelial cells of the respiratory tract results in a reduced capacity to secrete chloride ions to the airway surface and, indirectly, in an increased absorption of sodium ions from airway surfaces (Collawn *et al.*, 2012; O'Sullivan & Freedman, 2009). This imbalance of active ion transport favors the net removal of salt and concomitant water from airway surfaces. Loss of water in the gel-like periciliary layer results in a loss of lubrication of the airway surface and increased concentrations of mucin in the mucus layer. Dehydrated periciliary layer (PCL) leads to thicker mucus and cilia collapse, which results in a reduced mucociliary clearance. The 'stuck' mucus

ultimately creates an adhesive plaque, or ‘mucus plug’. These plaques stimulate inflammation, obstruct the airway lumen, produce airflow obstruction, and serve as a nidus for persistent bacterial infections. It is the same loss of CFTR-mediated ion regulation that leads to dysfunction in other organ systems, including the gastrointestinal (eg, malabsorption), biliary, pancreatic and sweat exocrine, reproductive (congenital bilateral absence of the vas deferens in males) systems.

QR-010 Product Description

QR-010 is under development for the chronic treatment of patients with CF that is associated with either a compound hetero- or homozygous genotype for the absence of $\Delta F508$ on CFTR-encoded RNA. The goal of treatment with QR-010 is repair of the CFTR region of the RNA encoded with the $\Delta F508$ mutation. Translation of the repaired CFTR encoded RNA should result in [REDACTED] normal CFTR protein. The intended route of clinical administration is inhalation of nebulized QR-010 solution, which is anticipated to result in both local effects to the respiratory system and systemic absorption. Hence, QR-010 has the potential to treat both pulmonary and extra-pulmonary manifestations of CF.

QR-010 was developed from a synthetic RNA oligonucleotide duplex that was described in a 2004 paper by [name], a pioneer of antisense therapeutics (Stephenson & Zamecnik, 1978, Zamecnik & Stephenson, 1978, Zamecnik *et al.*, 1986, Zamecnik *et al.*, 2004). [REDACTED]

[figure not shown]
[REDACTED] The Sponsor’s product development program explored various chemical modifications to the original molecule to optimize function (ability to restore CFTR activity [REDACTED]) in vitro and cellular uptake in vivo. The molecule selected for further development, QR-010, is a single-stranded, 33-mer RNA oligonucleotide with 2’O-Me base modifications and a full phosphorothioate (PS) backbone. QR-010 is highly specific for the CFTR RNA, with 14 and 16 complementary base-pairs on either side of the $\Delta F508$ deletion region, as confirmed using the basic local alignment search tool (BLAST) at the National Center for Biotechnology Information (search most-recently conducted 21 August 2014)¹.

As described above, QR-010 is a single-stranded 33-mer RNA oligonucleotide with 2’O-Me base modifications and a full PS backbone. QR-010 is highly specific for the CFTR RNA, with 14 complementary base pairs (bps) on the 5’ side and 16 complementary bps on the 3’ side of the $\Delta F508$ deletion region. To address the question of whether or not QR-010 was specific to this region of the CFTR RNA, a basic local alignment search tool (BLAST) at the National Center for Biotechnology Information was conducted and showed 100% specificity for this region. Repeated BLAST searches were completed, with the most recent conducted 21 August 2014.

¹ Available at <http://blast.ncbi.nlm.nih.gov/Blast.cgi>

Figure 2 illustrates the sequence that contains the ΔF508 mutation and the complementary hybridization of QR-010 to that region.

Figure 2: Hybridization of QR-010 to the ΔF508-CFTR RNA

Sequence with grey shading (C-U-U) on ΔF508 RNA represents the absence of phenylalanine at position 508 (ΔF508 mutation). Because both A-U-C (wild-type) and A-U-U (ΔF508) code for isoleucine, position 507's amino acid is unchanged, and the net effect of the 3 nucleotides missing in the ΔF508 mutation is omission of a phenylalanine ("F") at position 508 in the translated protein. Vertical bars represent the QR-010 binding region. Bold text (G-A-A) on QR-010 represents the complement of the missing C-U-U sequence.

